If it's not possible to conduct the baseline bone imaging, and/or dental examination, and/or dental imaging on the day of Visit 2, the procedure can be done in the 2 weeks (until study day 15) immediately after the visit. If it's not possible to conduct the follow-up bone imaging, and/or dental examination, and/or dental imaging on the day of the visit, the procedure can be done in the week immediately before or after the visit. Please refer to the image acquisition guideline available in the ISF for details.

¹⁷After the individual patient's end of the trial the investigator should report only any occurrence of cancer, study treatment related Serious Adverse Events (SAEs) and study treatment related Adverse Event of Special Interests (AESIs) of which the investigator may become aware of by any means of communication, e.g. phone call. Those AEs should be reported on the BI SAE form, but not on the eCRF. Please see [Section.5.2.7.2.1](#).

¹⁸Patients who prematurely discontinue trial medication will be asked to remain in the study and return to all regularly scheduled visits until the end of the trial. For those patients who are unable to complete the scheduled visits, every attempt will be made to get information on vital status at 24 weeks after randomization, i.e. the time of the data cut-off for the primary analysis of safety, at 52 weeks and at the end of the trial.

In the event of force majeure or other disruptive circumstances (e.g. pandemic) the investigational plan as per this clinical trial protocol may not be feasible at a site. With the consent of the patient's parent(s)/legal guardian (and assent by the patient where applicable), sponsor and investigator may implement risk mitigation measures and modifications to CTP standard procedures as described in [Appendix 10.9](#). See also [Section 4.1.4](#), [Section 6.1](#) and ISF for details.

FLOW CHART FOR PK BLOOD SAMPLING

| Visit | Week (±days) | Time Point [hh:min] | CRF Time /PTM | Event |
|----------|-----------------|------------------------|------------------|---------------------|
| (Part A) | 2 (±3) | -0:05 ¹ | -0:05 | PK Blood |
| | | 0:00 | --- | Drug administration |
| | | 1:00 ² | 1:00 | PK Blood |
| | | 2:00 ² | 2:00 | PK Blood |
| | | 3:00 ² | 3:00 | PK Blood |
| | | 4:00 ³ | 4:00 | PK Blood |
| | | 6:00 ³ | 6:00 | PK Blood |
| | | 8:00 ³ | 8:00 | PK Blood |
| (Part B) | 26 (±3) | -0:05 ¹ | -0:05 | PK Blood |
| | | 0:00 | --- | Drug administration |

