7.2.5 Safety analyses

Adverse events will be coded using the Medical Dictionary for Drug Regulatory Activities (MedDRA). Standard BI summary tables and listings will be produced. All adverse events with an onset between start of treatment and end of the REP, a period of 28 days after the last dose of trial medication, will be assigned to the on-treatment period for evaluation.

All treated patients will be included in the safety analysis. In general, safety analyses will be descriptive in nature and will be based on BI standards. No hypothesis testing is planned.

Statistical analysis and reporting of adverse events will concentrate on treatment-emergent adverse events, i.e. all adverse events occurring between start of treatment and end of the REP. Adverse events that start before first drug intake and deteriorate under treatment will also be considered as 'treatment-emergent'.

As this study consists of a double-blind, placebo-controlled part (Part A) and an open-label part (Part B), two treatment periods will be used for analysis and definition of ‘treatment-emergent’:

1. Double-blind period: Only adverse events assigned to the on-treatment period with onset during the double-blind period will be considered for the analysis.
2. Whole-trial period: All adverse events assigned to the on-treatment period will be considered for the analysis.

Frequency, severity, and causal relationship of adverse events will be tabulated by system organ class and preferred term after coding according to the current version of the Medical Dictionary for Drug Regulatory Activities (MedDRA) at database lock.

Laboratory data will be analysed both quantitatively as well as qualitatively. The latter will be done via comparison of laboratory data to their reference ranges. Values outside the reference range as well as values defined as clinically relevant will be summarised. Treatment groups will be compared descriptively with regard to distribution parameters as well as with regard to frequency and percentage of patients with abnormal values or clinically relevant abnormal values.

Vital signs, physical examinations, or other safety-relevant data observed at screening, baseline, during the course of the trial and at the end-of-trial evaluation will be assessed with regard to possible changes compared to findings before start of treatment.

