5.2.2 Secondary endpoint(s)

Endpoints will be used as defined in the CTP Section 2.1.3. Additional specifications are given below.

5.2.2.1 N (%) of patients with treatment-emergent pathological findings of epiphyseal growth plate on imaging at week 24, and week 52

Pathological findings which were already present at baseline imaging will NOT be considered treatment-emergent in this analysis, in spite identified after start of treatment, in order to be able to separate:

- findings that were identified on the follow-up MRI/x-ray and were already present on the baseline MRI/x-ray (i.e. not treatment-emergent)
- findings that were identified on the follow-up MRI/x-ray and were NOT already present on the baseline MRI/x-ray (i.e. treatment-emergent).

There are two possible kinds of predefined pathological findings for the growth plate recorded in the Safety Read Results:

- Pathological Findings at the Distal Femur
- Pathological Findings at the Proximal Tibia

A pathological finding of epiphyseal growth plate is defined as a pathological finding at the distal femur or the proximal tibia.

More precisely,

- Thickening of the epiphyseal growth plates
- Swelling of articular cartilage

will be captured as pathological findings.

Whereas,

- Narrowing of the lucent growth plate margin compared to the baseline time point (at post-baseline time points only)
- Metaphyseal lines
- Other findings

will only be captured as pathological findings if judged pathological.

Frequencies will be reported in a cumulative way over 24 and 52 weeks, respectively.

5.2.2.2 N (%) of patients with treatment-emergent pathological findings on dental examination or imaging at week 24, and week 52

Pathological findings which were already present at baseline imaging/examination will NOT be considered treatment-emergent in this analysis, in spite identified after start of treatment, in order to be able to separate:

- findings that were identified on the follow-up panoramic x-ray and were already present on the baseline panoramic x-ray (i.e. not treatment-emergent)
- findings that were identified on the follow-up panoramic x-ray and were NOT already present on the baseline panoramic x-ray (i.e. treatment-emergent).

For the dental examination, pathological findings will be identified through the dental examination eCRF pages where the question ‘Is this a new abnormal finding’ is answered with ‘Yes’ and thus, an AE page is filled in.

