If a baseline pathological finding is reported with a post-baseline worsening, it will be counted as treatment-emergent from the time point of worsening.

For the dental imaging, a pathological finding is defined as at least one tooth being reported in the Safety Read Results with at least one of the following findings:

1. Change in root length (at post-baseline time points only)
 - "Stunted growth (e.g., premature closing of the apex/apices with a blunted root appearance)"
 - "Accelerated growth (abnormally long roots exceeding 2/3rd the total length of the tooth)"
2. Extra/Supernumerary teeth
3. Impacted permanent teeth
4. Additional findings (“cyst present”, “abscess is present”, “solid lesion is present”, “bone abnormality is present”)
5. Additional findings “other findings” (incl. comment)

Frequencies will be reported in a cumulative way over 24 and 52 weeks, respectively.

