6.6.2.4 Endpoints based on MRI/x-ray

Patients will complete the baseline MRI/x-ray within the first 2 weeks after randomization. As for the imaging variables we do not expect a change through treatment within the first two weeks wherefore a measurement within the first two weeks can still be considered as baseline in this special case. The same holds for dental examination.

6.6.2.5 6-min walk test (6MWT)

In case the earliest assessment of the 6MWT is on treatment start day after treatment start time, then the whole 6MWT (pre-, during and after) assessment can still be counted as baseline assessment.

[figure not shown]

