7.8 SAFETY ANALYSIS

7.8.1 Adverse Events

Adverse events will be coded using the current Medical Dictionary for Regulatory Activities (MedDRA) version in use at BI at the time of database lock. The analyses of AEs will be descriptive in nature.

All analyses of AEs will be based on the number of patients with AEs and NOT on the number of AEs. To account for the variable length of exposure to treatment in both study periods tables will be presented including count and percentage of patients with AE and the incidence rates of AEs with time at risk and rate per 100 patient years. Please refer to [Section 7.8.1.1](#) for further details on the derivation of time at risk and exposure-adjusted incidence rates.

Since this study consists of a double-blind, placebo-controlled part and an open-label part with nintedanib treatment only, three treatment periods will be used for analysis and definition of “treatment-emergent”:

- 1. Double-blind period:** Analyses of AEs will be presented by treatment group and overall. Only adverse events with onset or worsening on or after date of treatment start until end of double-blind period (defined as the day before first intake of open-label nintedanib or last double-blind drug intake + residual effect period, whichever is earlier) will be considered as treatment-emergent and will be included in the analysis. Adverse events will be counted under the treatment as randomized for the double-blind period.
- 2. Nintedanib exposure period:** Analyses of AEs will be presented by randomized treatment group and overall. All adverse events with onset or worsening on or after first intake of nintedanib (double-blind or open-label period) until last intake of nintedanib (double-blind or open-label period) + residual effect period will be considered as treatment-emergent and will be included in the analysis.

3. Over the whole-trial: Analyses of AEs will be presented by treatment group and overall. All adverse events with onset or worsening on or after date of treatment start until last drug intake + residual effect period will be considered as treatment-emergent and will be included in the analysis. Adverse events will be counted under the treatment as randomized for the double-blind period.

In case an AE starts on first day of open-label treatment, it is assigned to the open-label period (and not to the double-blind period).

For further details on summarization of AE data, please refer to ([8](#), [17](#)).

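### SAP 5.2.2.1 has no rule for worsening of a growth-plate finding seen at baseline, so the secondary bone endpoint leaves out progression that the AE tables would count

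*SAP*

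**What the plan says.** SAP 5.2.2.1 sorts follow-up growth-plate findings into two groups. The first is excluded: "Pathological findings which were already present at baseline imaging will NOT be considered treatment-emergent in this analysis". The second is counted: "findings that were identified on the follow-up MRI/x-ray and were NOT already present on the baseline MRI/x-ray (i.e. treatment-emergent". Thickening of the growth plate and swelling of articular cartilage always qualify as pathological. Metaphyseal lines, other findings and one comparative item qualify only if judged pathological. The comparative item is "Narrowing of the lucent growth plate margin compared to the baseline time point (at post-baseline time points only". Frequencies are cumulative over 24 and 52 weeks.

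SAP 5.2.2.2 opens with the same exclusion for teeth. After the paragraph on dental examination it adds: "If a baseline pathological finding is reported with a post-baseline worsening, it will be counted as treatment-emergent from the time point of worsening".

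For adverse events, protocol 7.2.5 says: "Adverse events that start before first drug intake and deteriorate under treatment will also be considered as" treatment-emergent. SAP 7.8.1 uses onset or worsening in each of its three analysis periods; for the whole trial it reads "All adverse events with onset or worsening on or after date of treatment start until last drug intake + residual effect period".

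On timing of the baseline image, the protocol Flow Chart notes allow that "the procedure can be done in the 2 weeks (until study day 15) immediately after the visit". SAP 6.6.2.4 accepts this: "a measurement within the first two weeks can still be considered as baseline in this special case". Table 6.7: 4 sets the baseline window for bone imaging at day -84 to day 15. Its second footnote takes a pre-dose image where one exists and a post-dose image only where none does.

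**The concern.** Under the two-way split, a child whose baseline image shows thickening, and whose thickening clearly progresses on nintedanib, falls in the group that is not treatment-emergent. Elsewhere the plan counts deterioration, and SAP 5.2.2.1 gives no reason for treating bone differently.

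Growth-plate change is one of the paediatric risks named in protocol Table 1.4.2:1, on the basis of animal findings in femur and tibia. Pathological findings on bone imaging are an AESI. The baseline image is taken in children who have already qualified for randomisation, so an abnormal growth plate does not by itself keep a child out. The same child could therefore appear in the AESI table for a worsened bone finding and be counted as having no treatment-emergent finding in the endpoint built to describe that risk.

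**Working it through.** The plan gives no figure to reproduce here, so the check is mainly a comparison of rules.

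**1. Is worsening of a baseline finding treatment-emergent?**

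| Output | Source | Worsening counts? |
|---|---|---|
| Growth-plate endpoint | SAP 5.2.2.1 | No rule; present at baseline means not counted |
| Dental endpoint | SAP 5.2.2.2 | Yes for clinical examination; reach to dental imaging unclear |
| Adverse events | Protocol 7.2.5 | Yes |
| Adverse events, all three periods | SAP 7.8.1 | Yes |

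**2. What still counts inside the growth-plate endpoint?** Narrowing is defined against baseline and counts if judged pathological. A different kind of finding that was absent at baseline also counts. What is left out is progression of the same finding: thickening, cartilage swelling, metaphyseal lines or an item under other findings.

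**3. Where would that progression appear?** Protocol 5.2.7.1.1 asks for growth-plate findings, and for worsening of pre-existing conditions, to be recorded as AEs. SAP 7.8.1.4 sends AEs identified on imaging to the standard AE tables. A reported worsening is therefore analysed there, but not in the endpoint.

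**4. Late baseline image.** For a child with no pre-dose image, a change visible by day 15 is classed as baseline. By step 1 its later progression is not counted either, unless it shows as narrowing or as a new kind of finding.

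**5. Size per child.** The protocol synopsis plans about 20 nintedanib and 10 placebo patients. SAP 7 sets percentages on all patients in the set unless otherwise specified, and 5.2.2.1 specifies nothing else. One nintedanib child is 1/20 = 5 percentage points.

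**6. Illustration of frequency (assumed inputs).** Let b be the share of children with a baseline finding, and w the share of those in whom that finding worsens with nothing else countable. The documents give neither. With independent patients, all 20 followed by imaging:

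- expected uncounted children = 20 × b × w
- chance of at least one = 1 − (1 − b × w)^20

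| b | w | Expected uncounted | Chance of at least one |
|---|---|---|---|
| 5% | 10% | 0.1 | 9.5% |
| 10% | 25% | 0.5 | 39.7% |
| 20% | 25% | 1.0 | 64.2% |
| 30% | 50% | 3.0 | 96.1% |

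Follow-up imaging is limited to children with open physes, so the number who can be affected may be below 20. The spread shows that frequency cannot be settled from the documents.

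**The case against.** The strongest reply is that the information is not lost. SAP 7.8.1 and 7.8.1.4 count a worsened growth-plate finding reported as an AE, AESI tables are planned, and the SMC sees the bone images whatever this endpoint shows. A reader might infer that the SAP never counts worsening of a baseline bone finding, or that the endpoint cannot detect deterioration. Neither is supported: the AE tables count it, and narrowing and new kinds of finding count within the endpoint.

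The dental comparison is also imperfect. The worsening sentence comes before the list of dental imaging findings, and the panoramic x-ray bullets use the same present-or-absent split as bone. Both centrally read endpoints may be handled alike. That weakens the parallel with teeth but leaves the contrast with the AE definition intact.

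On the late baseline, a post-dose image is only a fallback, and SAP 6.6.2.4 discloses its premise that imaging should not change in two weeks. This limits how many children are affected; it does not supply a rule for those who are.

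Finally, the endpoint is descriptive, the rule applies to both arms, and separating new from pre-existing findings is its stated purpose. All true. A separate row for worsened findings keeps that purpose and removes the conflict with the AE tables.

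**Conclusion.** The point holds for the secondary endpoint in SAP 5.2.2.1, and only there. Progression of a baseline growth-plate finding, other than narrowing judged pathological, is left out of that endpoint and appears in the AE and AESI tables only if it is reported. The omission can only lower the count. If nintedanib causes such progression, it hides cases on the active arm, which is why the endpoint leans towards no bone harm.

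Each affected child moves the nintedanib percentage by 5 points, assuming 20 patients in the denominator. A reader might prefer children with open physes as the denominator, which would make each child weigh more, but the SAP's default does not support that and the number with open physes is not given. How many children are affected is unknown; the frequencies in the illustration rest wholly on assumed rates. The wording should be corrected because the risk is a named one and the change is small, but AE capture and SMC review of bone safety do not depend on it.

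**What to change.** Add one sentence to SAP 5.2.2.1: a growth-plate finding present at baseline that worsens afterwards is counted as treatment-emergent from the time of worsening. Worsening would be established by an AE report of worsening, or by the central reader's record if the read form captures it. Show new and worsened findings in separate rows, so that the split the section aims for stays visible. If bone is meant to be treated differently, say why, and note under the table that worsening appears only in the AE tables.

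The cost is one sentence and one table row. It should not be assumed that no extra reading is needed: the SAP describes comparison with baseline only for narrowing. If the central read does not grade progression of thickening or swelling, the worsened row will rest on AE reports, and a footnote should say so.

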5.2.2.3 N (%) of patients with treatment-emergent adverse events over the whole trial

The analysis will include all adverse events during the double-blind and open-label periods of the trial, see [Section 7.8.1](#).

5.2.2.4 Change in height, sitting height, leg length from baseline at week 24, and week 52, week 76, and week 100

The absolute change from baseline in height, the absolute change from baseline in sitting height and the absolute change from baseline in leg length will each be computed and evaluated separately.

As the sitting height has been measured incorrectly (i.e. total distance between the floor and the top of patient’s head with the patient in a sitting position) at some sites ([2](#)), the main analysis of this endpoint will contain only the correctly measured (i.e. total distance between the sitting surface and the patients top of patient’s head with the patient in a sitting position).

5.2.2.5 Change in Forced Vital Capacity (FVC) % predicted from baseline at week 24, and week 52

The absolute change from baseline in FVC % predicted (percent of predicted) at week 24 and week 52 will be used. The predicted values are calculated by the vendor according to Global Lungs Initiative (GLI) 2012 equations (4).

5.2.2.6 Absolute change from baseline in Pediatric Quality of Life Questionnaire (PedsQL) at week 24, and week 52

Health-related quality of life will be assessed using the PedsQL™ questionnaire. Depending on the age there are PedsQL™ Young Child Report (ages <8 years), Child Report (ages 8-12 years) and Report for Teens (ages >13.0 years). Furthermore, the respective Parent Reports are filled in by the parents of the child. For more details see CTP Section 5.6.1.

The questionnaire consists of 23 items and 4 dimensions: physical functioning, emotional functioning, social functioning and school functioning.

The PedsQL™ evaluation will primarily focus on the absolute change from baseline in the total score at week 24, and week 52.

In addition, the absolute change from baseline in the psychosocial health summary score (sum of emotional, social, and school functioning scales) and the absolute change from baseline in the physical health summary score (physical functioning score) will be presented.

A 5-point Likert response scale (0 = never; 1=almost never; 2=sometimes; 3=often; 4=almost always) is used in all cases except for the Young Child Report, where a 3-point scale (0=not at all; 2=Sometimes; 4=a lot) is used.

Items are reverse-scored and linearly transformed to a 0-100 scale (0 = 100, 1 = 75, 2 = 50, 3 = 25, 4 = 0), so that higher scores indicate better health-related quality of life (HrQoL).

The specific instructions for deriving the PedsQL™ total score are provided in [Appendix Section 9.1](#).

5.2.2.7 Change in oxygen saturation (SpO₂) on room air at rest from baseline at week 24, and week 52

Oxygen saturation on room air at rest will be analysed.

5.2.2.8 Change in 6-min walk distance from baseline at week 24, and week 52

The exercise capacity of the patient will be recorded as distance covered in 6 minutes on the respective eCRF page. Furthermore, continuous pulse oximetry (SpO₂) will be performed and additional measurements such as pulse rate and blood pressure conducted.

The 6-minute walk test evaluation will primarily focus on the absolute change from baseline in the distance walked. Oxygen saturation measured by SpO₂, vital signs and BORG CR-10 Scales of the patient will be presented as scatterplots (each parameter versus age).

Only one value per period (pre-test, during test, post-test and recovery) patient, parameter and visit will be shown: for pulse rate, blood pressure and BORG scales the highest; for oxygen saturation and walking time the lowest value.

For more details please refer to CTP Section 5.1.6.

5.2.2.9 Patient acceptability based on the size of capsules at week 24

The acceptability questionnaire will be filled in by the patient. Further, to collect the investigator / site staff impression about the patient's acceptability of the study medication intake, the treatment acceptability questionnaire for the investigator or investigational site staff will be completed by the investigator / site staff.

The answer to question 3 on the patient's questionnaire "How is the size of the capsule" of the "Acceptability Questionnaire for the patient" will be used with categories "OK (=acceptable)", "Large", "Very large".

On the investigator questionnaire, the question 3 "If the drug was not taken, was this due to (check all answers that you consider applicable for this patient at this point in time" and others will be assessed to retrieve more information on the acceptability and palatability of the capsules.

An analysis of patients not taking the 100 mg b.i.d. or 150 mg b.i.d. form, i.e. who take 4x25 mg b.i.d. or 6x25 mg b.i.d., will be conducted in order to examine the swallowability.

5.2.2.10 Patient acceptability based on the number of capsules at week 24

The answer to question 4 "How easy was to swallow the given number of capsules" of the "Acceptability Questionnaire for the patient" will be used with categories "I had no problem swallowing them (=acceptable)", "I swallowed them, but it was difficult", "I could not swallow them sometimes".

See also [Section 5.2.2.9](#).

